For the primary efficacy endpoint, a minimum of 172 subjects are needed in each treatment arm to detect non-inferiority of bexagliflozin to glimepiride with respect to the change in HbA1c from baseline at week 60 by a margin of 0.35%, assuming an estimated pooled standard deviation of 1.0%. This estimation is based on a one-sided t-test with 90% power at a 0.025 level of significance. To allow for an estimated 18.0% dropout rate, 210 patients will be randomized in each treatment arm, and the total sample size will be 420 subjects for this study.

Statistical analyses and summaries will be performed using SAS[®] software (SAS Institute, Cary, NC).

LIST OF ABBREVIATIONS AND DEFINITIONS OF TERMS

ADA	American Diabetes Association
AE	adverse event
ALB	albumin
ALT	alanine aminotransferase
ANCOVA	analysis of covariance
AST	aspartate aminotransferase
ATC	Anatomic Therapeutic Chemical classification
BMI	body mass index
BP	blood pressure
BUN	blood urea nitrogen
CEC	cardiovascular endpoint committee
CFR	Code of Federal Regulations
CI	confidence interval
CRF	case report form
CRO	contract research organization
DKA	diabetic ketoacidosis
CYP	cytochrome P450
DPP4	dipeptidyl peptidase-4
DSMB	data and safety monitoring board
ECG	electrocardiogram
eGFR	estimating glomerular filtration rate
FPG	fasting plasma glucose
GCP	Good Clinical Practice
GI	gastrointestinal
GLP-1	glucagon-like peptide-1
GMI	genital mycotic infection
h	hour
HbA1c	hemoglobin A1c
HBsAg	hepatitis B surface antigen
Hct	hematocrit
HCV	hepatitis C virus
HDL-C	high density lipoprotein cholesterol
HDPE	high-density polyethylene
Hgb	hemoglobin
HIV	human immunodeficiency virus
ICH	International Conference on Harmonisation

IEC	independent ethics committee
IND	Investigational New Drug application
IRAE	immediately reportable adverse event
IRB	institutional review board
ITT	intention-to-treat
IWRS	Interactive Web Response System
LDL-C	low density lipoprotein cholesterol
LOCF	last observation carried forward
MACE	major adverse cardiovascular event
MCH	mean corpuscular hemoglobin
MCHC	mean corpuscular hemoglobin concentration
MCV	mean corpuscular volume
MDRD	modification of diet in renal disease
MedDRA	medical dictionary for regulatory activities
MI	myocardial infarction
MMRM	mixed model repeated measures
MODY	maturity-onset diabetes of the young
N	number of subjects
NYHA	New York Heart Association
OHA	oral hypoglycemic agent
PO	per oral
PP	per protocol

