3.8. DETERMINATION OF SAMPLE SIZE

An approximate total of 420 subjects will be randomized and equally allocated to receive:

- bexagliflozin tablets, 20 mg and glimepiride, placebo capsules (referred to as bexagliflozin group in this document)
- bexagliflozin tablets, placebo and glimepiride capsules, 2 mg, 4 mg, or 6 mg (referred to as glimepiride group in this document).

The sample size calculation for this study is based on a two group t-test with a one-sided significance at the 0.025 level and the following assumptions:

- The non-inferiority limit (margin) for mean change from baseline to week 60 in HbA_{1c} comparing bexagliflozin group to glimepiride group will be 0.35%
- The standard deviation for the change from baseline to week 60 in HbA_{1c} for bexagliflozin group and glimepiride group will be 1.0%

Under the above assumptions, an estimated sample size of 172 subjects is needed in each treatment arm to determine non-inferiority of bexagliflozin to glimepiride with respect to change in HbA_{1c} at week 60 from baseline. This estimation is based on a one-sided t-test with 90% power at a 0.025 level of significance. A sample size of 210 per arm has been selected to account for approximate 18% drop-out rate and to allow adequate safety evaluation. The total sample size for this study will be 420 subjects.

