3.9. TREATMENT ASSIGNMENT & BLINDING

3.9.1. Treatment Assignment

The study will be conducted at multiple investigative sites and will likely involve various numbers of subjects at each site. The study will have a competitive enrollment but the number of randomized subjects from each site will be capped at 40. Activation of investigational sites will be centrally controlled by an Interactive Web Response System (IWRS). Subject randomization will be deactivated for all sites when the planned number of subjects is met. However, if a potential subject is in wash-out already and wishes to continue with the study, the subject will be allowed to continue and, if eligible, to be randomized.

Eligible subjects who have completed the wash-out of oral hypoglycemic agent other than metformin and have met all study inclusion/exclusion requirements are to be randomized in a 1:1 ratio to receive active bexagliflozin with placebo glimepiride or active glimepiride with placebo bexagliflozin. Subjects will be assigned to treatment groups in sequential order as they qualify for the study. Randomization will be stratified according to baseline (Visit V5) HbA_{1c} (< 8.5% or ≥ 8.5%), treatment background

(metformin-only or metformin-and-OHA), and Visit V5 eGFR (≥ 90 or < 90 and ≥ 60 mL/min/1.73 m²).

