If no sufficient week 60 values from treatment discontinued subjects are available for imputation, MMRM analysis as in step 3 will be performed using all available data.

Sample SAS code will be provided in Appendix.

In non-inferiority analysis, a CI is calculated to estimate the range of values in which the treatment difference is likely to lie. This CI is used to provide the basis for drawing the study's conclusions. In this specific test, if the 95% CI lies below the specified non-inferiority margin 0.35%, the results would lead to a conclusion of non-inferiority of

bexagliflozin treatment to glimepiride treatment. Lower HbA_{1c} value indicates improvement on subject diabetes condition. Larger decrease would indicate better treatment effect of bexagliflozin compared to glimepiride. Hence, superiority of bexagliflozin group over glimepiride group at week 60 in HbA_{1c} change from baseline will be declared if the upper bound of 95% CI is less than 0.

Descriptive statistics (n, mean, Q1, median, Q3, SD, minimum, and maximum) will be reported by treatment group and visit, along with the least squares means, differences between LS means, a 2-sided 95% confidence interval for each difference, p-values from the model effects. In addition, the LS means with standard errors of the change from baseline over time and difference between treatment groups with 95% will be presented graphically for the ITT population.

For supportive analyses, regardless of having sufficient week 24 values from treatment discontinued subjects are available for imputation or not, MMRM analysis will be performed using all available data. The primary efficacy endpoint will also be analyzed with all observed available data using MMRM method for the PP analysis set.

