8.1.2. Sensitivity Analyses

Randomized subjects who withdraw consent to participate in the study will not be replaced. The early withdrawal rate is estimated to be 18%. To the extent possible, attempts will be made to minimize the amount of missing data through measures planned in the study conduct.

To investigate the possible implications of missing values in efficacy assessments, the number, timing, pattern, and reason for the missing value will be summarized. The reason for withdrawal will be reviewed. If there are missing values for the primary analysis described in section 8.1.1, only available data will be analyzed and data obtained after rescue will not be excluded.

The dropout patterns will be assessed by a Kaplan-Meier plot of time to discontinuation by treatment group to assess whether they differ between treatment groups.

To evaluate the impact from missing data and rescue medication, the following sensitivity analyses will be conducted:

- 1) Tipping point analysis will be conducted. Data after rescue medication will be considered as missing. The following steps will be implemented:
 - a. Create monotone missing data as step a in the primary analysis in section 8.1.1 with 100 imputed datasets;
 - b. Regression approach under MAR will be used to generate complete datasets. The predictors for the regression imputation model at any time point will be region,

treatment background (metformin only or metformin and OHA), baseline eGFR (≥ 90 or < 90 mL/min/1.73 m²), treatment, and HbA_{1c} at all previous time points, including baseline. The first imputed values will be penalized or rewarded based on the treatment subject received:

- Subjects in the bexagliflozin group: missing value will be analyzed assuming the treatment effect is worsened by δ_1 (where $\delta_1 = 0.1$ to 0.5 , in step of 0.1) compared to the subjects who have no missing value in the reduction of HbA_{1c} value;
- Subjects in the glimepiride group: missing value will be analyzed assuming the treatment effect is better by δ_2 (where $\delta_2 = 0.1$ to 0.5 , in step of 0.1) compared to the subjects who have no missing value in the reduction of HbA_{1c} value;

The penalty or reward will not be applied to the values from later time points as these values are penalized or rewarded through regression on previous time points.

- c. Imputed datasets will be analyzed and results combined as step 3 in section 8.1.1.

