For each combination of (δ_1 , δ_2), 100 imputed datasets will be obtained. These 25 combinations will be separately analyzed to explore under which condition where the null hypothesis can no longer having evidence to be rejected.

- 2) Additionally, the impact of the data after the start of rescue medication will be evaluated. HbA_{1c} values collected after the start of rescue medication will be considered missing, and the MMRM analyses will be performed. Same statistics provided for the primary analysis will be presented.

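### The tipping-point delta in SAP 8.1.2 is added only at the first imputed visit and is diluted by week 60, and the capped grid may end without a tipping point

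*SAP*

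**What the plan says.** SAP 8.1.2 lists a tipping-point analysis as its first sensitivity analysis for the primary endpoint. Post-rescue HbA1c values are set to missing. Gaps are filled under missing at random (MAR) by sequential regression on all earlier HbA1c values, including baseline. The first imputed value is then shifted. In the bexagliflozin arm a "missing value will be analyzed assuming the treatment effect is worsened by" δ1; in the glimepiride arm it is taken as better by δ2. For the visits that follow, "The penalty or reward will not be applied to the values from later time points", the stated reason being that regression on the shifted value already carries the effect forward.

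Each delta runs from 0.1 to 0.5 in steps of 0.1. "These 25 combinations will be separately analyzed to explore under which condition where the null hypothesis can no longer having evidence to be rejected". There is no cell with a delta of zero in either arm, and nothing says what happens if no cell reverses the conclusion.

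The conclusion being tested is the week-60 one in SAP 8.1.1: non-inferiority holds "if the 95% CI lies below the specified non-inferiority margin 0.35"%. SAP 13 drops the protocol's last-observation-carried-forward analysis on the ground that it adds nothing beyond the tipping-point analysis.

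**The concern.** The delta matters only through the week-60 value. The regressions that carry it forward also use earlier observed values, which carry no penalty, so under any ordinary pattern of visit correlations only part of it survives. A reader of the (0.5, 0.5) cell would naturally take it that dropouts were assumed 0.5 worse or better at week 60. That is true only for subjects first missing at week 60.

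The grid also stops at a fixed limit. If no cell tips, the report contains no tipping point, and the result may be taken as robustness to departures from MAR larger than those examined. This weighs most if too few treatment-discontinued subjects have week-60 values. SAP 8.1.1 then falls back to a mixed model on available data, and this grid becomes the only explicit missing-not-at-random check on the HbA1c claim.

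**Working it through.** **Inputs from the documents**
- Margin 0.35 (SAP 8.1.1).
- SD of change 1.0: "assuming an estimated pooled standard deviation of 1.0"% (Protocol synopsis).
- Error rate and power: "This estimation is based on a one-sided t-test with 90% power at a 0.025 level of significance" (SAP 3.8).
- Size: "an estimated sample size of 172 subjects is needed in each treatment arm", and 210 per arm randomised for about 18% dropout (SAP 3.8). Allocation is 1:1 (SAP 3.9.1).
- Early withdrawal 18% (SAP 8.1.2).
- HbA1c visits: baseline and weeks 12, 24, 36, 48 and 60.

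**Assumptions, not in the documents**
- Visit correlations of 0.5 to 0.9, either autoregressive (AR) or equal.
- First missing visit spread evenly over weeks 12 to 60, with the same missing share in both arms.
- Missing share 18%, or 25% to 30% once post-rescue values are removed (no rescue rate is given).
- Standard error fixed at its planned value.
- True difference 0, which the plan's own sample size implies.

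**1. The plan's figure.** n per arm = 2 × (1.960 + 1.282)² × 1.0² / 0.35² = 171.6, so 172. Then 172 / 0.82 = 209.8, so 210. Both reproduce.

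**2. Room to the margin.** SE = √(2/172) = 0.108. The CI half-width is 1.96 × 0.108 = 0.211. At an estimate of 0, the upper bound is 0.35 − 0.211 = 0.139 short of the margin.

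**3. Share of the delta left at week 60.** A unit shift at the first missing visit was passed through the sequential regressions on all earlier visits.

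| Correlation | First missing at wk 12 | wk 24 | wk 36 | wk 48 | wk 60 | Average |
|---|---|---|---|---|---|---|
| AR 0.5 | 0.06 | 0.13 | 0.25 | 0.50 | 1.00 | 0.39 |
| AR 0.7 | 0.24 | 0.34 | 0.49 | 0.70 | 1.00 | 0.56 |
| AR 0.9 | 0.66 | 0.73 | 0.81 | 0.90 | 1.00 | 0.82 |
| Equal 0.5 | 0.33 | 0.25 | 0.20 | 0.17 | 1.00 | 0.39 |
| Equal 0.9 | 0.47 | 0.32 | 0.24 | 0.20 | 1.00 | 0.45 |

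The average runs from 0.39 to 0.82.

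**4. Largest shift the grid can produce.** Shift = missing share × (δ1 + δ2) × share left. At 18% missing in the (0.5, 0.5) cell:
- as written, 0.18 × 1.0 × 0.39 = 0.07 up to 0.18 × 1.0 × 0.82 = 0.15;
- with the delta in full at week 60, 0.18 × 1.0 = 0.18.

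To use up 0.139 at an estimate of 0, δ1 + δ2 must be 0.139 / 0.18 = 0.77 with the full delta, which lies inside the grid. As written, dividing by 0.82 or 0.39 gives about 0.94 to 1.99, against a grid limit of 1.0.

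**5. Chance that the grid finds a tip, given that non-inferiority was met.** With estimate ~ Normal(0, 0.108²), P(success) = Φ(0.139/0.108) = 0.901. P(tip | success) = 1 − Φ((0.139 − shift)/0.108) / 0.901.
- Shift 0.07: 1 − 0.738/0.901 = 18%.
- Shift 0.147: 1 − 0.468/0.901 = 48%.
- Shift 0.18: 1 − 0.351/0.901 = 61%.

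| True difference | Missing | As written | Full delta at week 60 |
|---|---|---|---|
| 0 | 18% | 18–48% | 61% |
| 0 | 25% | 28–70% | 83% |
| 0 | 30% | 35–82% | 93% |
| −0.1 | 18% | 5–19% | 28% |
| +0.1 | 18% | 40–75% | 85% |

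With SD 0.8 in place of 1.0, at 18% missing and a true difference of 0, the as-written range falls to about 9–32%.

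**6. Check by simulation.** Multiple imputation in 120 simulated trials per scenario gave 8–31% as written against 45–60% with the full delta at 18% missing, and 32–64% against 93–95% at 30%. These run somewhat below the formula at 18% missing because the simulated SD of change was at or below 1.0. The contrast is the same.

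**The case against.** The best defence is that the rule is disclosed. The SAP says that the first imputed value is shifted and that later ones move only through regression. SAP 8.2.4 uses the same convention for body weight and blood pressure. A reader might infer an internal error; the text does not support that. It is a coherent choice whose nominal delta is easy to misread.

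A reader might also infer that the grid cannot tip. The figures rule that out: 18–48% of successful trials tip in the planned case, and possibly more than half if post-rescue values lift the missing share. The 0.5 cap alone is not the cause in the planned case, since an undiluted delta would tip at a sum of 0.77.

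Nor are the departures trivial. At the extreme cell, missing subjects in the two arms still diverge by 0.39 to 0.82 at week 60, more than the 0.35 margin. A clearly non-inferior result ought to survive plausible deltas, so part of the low rate at a true difference of −0.1 is genuine robustness.

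This is also not the only safeguard in every case. When at least 3% per arm are retrieved, the primary analysis is itself a pattern-mixture model that imputes separately for early terminators. The missing zero is partly covered by the second sensitivity analysis, a mixed model with post-rescue values removed.

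All of this stands. What remains is that the nominal delta overstates what is tested at week 60, and that the plan gives no next step if no cell tips.

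**Conclusion.** The concern holds as a weak choice in a sensitivity analysis. For subjects whose data stop before week 60, the penalty at week 60 is on average about 39% to 82% of the nominal delta. In the planned case (18% missing, true difference 0, SD 1.0) this lowers the chance of finding a tipping point after a successful trial from about 61% to about 18–48%. At 25% missing the as-written range is about 28–70%.

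The direction of the dilution follows from the rule under the correlation patterns examined. Its size rests on the assumed correlations, evenly spread dropout, equal missingness in the two arms and a fixed standard error. The consequence is greatest if the retrieved-dropout primary analysis cannot be run. The primary test is unaffected.

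**What to change.** In SAP 8.1.2:
- Impute under MAR, then apply the delta so that it is present in full at week 60. Alternatively, keep the first-value rule and report the effective week-60 shift for every cell.
- Include a delta of zero in each arm, so that the grid contains the MAR result and can penalise bexagliflozin alone.
- Extend the grid until the upper 95% bound reaches 0.35, and report that boundary so that its clinical plausibility can be judged. As a guide, at 18% missing a full delta of up to 1.0 per arm shifts the difference by 0.18 × 2.0 = 0.36 and would find a tip in about 98% of successful trials at a true difference of 0.

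The cost is SAP wording, a larger grid and more programming. No new data are needed. This is a cheap improvement.

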8.1.3. Subgroups

Descriptive and MMRM model comparison using all available data for the primary endpoint will be repeated by subgroups. The nominal p-value will be presented without adjustment to the multiple comparisons. They are not used for inferential purpose. The subgroups include:

- Age (< 65 years or ≥ 65 years)
- Gender (male or female)
- Race (white or Caucasian; black or African-American; other)
- Baseline HbA_{1c} ($< 8.5\%$ or $\geq 8.5\%$)
- Treatment background (metformin-only or metformin-and-OHA)
- Baseline eGFR (≥ 90 or < 90 mL/min/1.73m²)

- Region

8.2. SECONDARY EFFICACY ENDPOINT(S) AND ANALYSES

The secondary endpoints will only be tested when the non-inferiority of the primary efficacy assessment is established at one-sided significance level of 0.025. To control the overall type I error of 0.05, the secondary efficacy objectives will be tested at one-sided 0.025 significance level following the sequence below:

- Superiority test of the change in body weight in subjects with baseline body mass index (BMI) ≥ 25 kg/m² at week 60.
- Superiority test of the change in SBP in subjects with baseline SBP ≥ 140 mmHg from baseline at week 60.
- Superiority test of the difference in proportion of subjects with ≥ 1 severe or documented symptomatic hypoglycemia events over 96 weeks

Analysis for secondary endpoints will be based on ITT analysis set and repeated for PP analysis set. For body weight and SBP, all post-baseline values up to week 60 will be used for model analysis. All values will be summarized.

8.2.1. Change in body weight in subjects with baseline body mass index (BMI) ≥ 25 kg/m² at week 60

This will be tested if the non-inferiority of HbA_{1c} and the previous secondary efficacy endpoints are significant. Data after rescue medication will not be excluded. The comparison of change in body weight between randomized treatments at week 60 will be carried out using the similar MMRM model as section 8.1.1 using all available data. The model will include terms for region, treatment, baseline HbA_{1c} as continuous variable, treatment background (metformin-only or metformin-and-OHA), and baseline eGFR (≥ 90 or < 90 mL/min/1.73 m²) as fixed effects and the corresponding baseline weight value as covariate. Treatment comparison p-values and difference at week 60 will be estimated from the model, with the two-sided 95 % CIs of the treatment difference also presented. If the superiority of HbA_{1c} is not established, the nominal p-value will not be used for inferential purposes. Summary table will be presented and figures will be displayed for ITT population.

8.2.2. Change in SBP in subjects with baseline SBP ≥ 140 mmHg from baseline at week 60

This will be tested if the change from baseline body weight is significantly different between bexagliflozin and glimepiride groups based on ITT analysis set for subjects with a BMI ≥ 25 kg/m². Change from baseline in SBP at week 60 will be analyzed in a similar manner as change in body weight, Section 8.2.1, based on ITT analysis set for all

subjects. Baseline SBP will be used in place of baseline weight. Summary table will be presented and figures will be displayed for ITT population.

8.2.3. Difference in proportion of subjects with ≥ 1 severe or documented symptomatic hypoglycemia event over 96 weeks

This will be formally tested if the previous secondary efficacy endpoints are significant. Events after the start of rescue medication will be counted. Descriptive statistics of frequency and percentage will be provided. Logistic regression model will be used, with region, treatment, baseline HbA_{1c}, treatment background (metformin-only or metformin-and-OHA), and baseline eGFR (≥ 90 or < 90 mL/min/1.73 m²) as fixed effects. Odd ratio estimates, 95% two-sided confidence intervals and p-values for the treatment difference will be provided. Summary table will be presented and figures will be displayed for ITT population.

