1. Missing data will be imputed via multiple imputations, following which the MMRM will be repeated on the complete datasets with results combined across complete datasets using standard multiple imputation techniques; HbA1c values collected after the start of rescue medication will not be excluded.
2. Missing data will be imputed via LOCF, following which the MMRM will be repeated; HbA1c values collected after the start of rescue medication will be considered missing.
3. HbA1c values collected after the start of rescue medication will be considered missing,

and the MMRM analyses will be re-performed.

The effects of bexagliflozin on the changes from baseline at week 60 in body weight and systolic blood pressure, the difference in the proportion of subjects with ≥ 1 severe or documented symptomatic hypoglycemia events over 96 weeks and the change in HbA1c from baseline at week 60 will be tested as key secondary endpoints and will be analyzed in a hierarchical testing strategy and only if the primary objective is met. Similar to the primary endpoint, ANCOVA models will be used for the continuous secondary endpoints and logistic regression model will be used for the binary endpoint. A hierarchical testing strategy will be followed to preserve experiment-wide alpha at 0.05:

1. Superiority test of the change in body weight in subjects with baseline BMI ≥ 25 kg/m² in the bexagliflozin group vs. the glimepiride group at week 60
2. Superiority test of the change in systolic blood pressure (SBP) in subjects with baseline SBP ≥ 140 mmHg in the bexagliflozin group vs. the glimepiride group at week 60
3. Superiority test of the difference in proportion of subjects with ≥ 1 severe or documented symptomatic hypoglycemia event in the bexagliflozin group vs. the glimepiride group over 96 weeks

Additional effects of bexagliflozin versus glimepiride on the changes in HbA1c, FPG, SBP, body weight, the proportion of subjects who reach an HbA1c $< 7\%$, and the proportion of subjects with ≥ 1 severe or documented symptomatic hypoglycemia events over time, as well as the general safety in subjects with T2DM, will be analyzed as exploratory efficacy endpoints. These endpoints are considered exploratory and will not be adjusted for multiplicity.

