9 PLANNED STATISTICAL METHODS

9.1 General Considerations

The following sections provide a summary of the planned analysis of the trial but a complete statistical analysis plan will be developed as a separate document and will be the final plan. All statistical analyses will be performed using SAS Version 9.2 or higher.

In general, descriptive statistics (number of subjects [N], mean, standard deviation [SD], Q1, median, Q3, minimum and maximum) will be presented for continuous variables, and frequency and percentage for categorical variables.

The primary efficacy non-inferiority test will be one-sided at 0.025 significance level. The upper bound of the 95% confidence interval (CI) on the difference of HbA1c reduction between bexagliflozin and glimepiride will be used to determine the study's conclusion. That is, if the upper bound of the CI is within 0.35%, then the primary objective of the study is met. Superiority will be declared without additional statistical testing when the upper bound of the 95% CI for the difference in change from baseline at week 60 in HbA1c comparing bexagliflozin group with glimepiride group is less than 0.

The secondary efficacy objectives will be tested at two-sided 0.05 significance level following a sequential testing procedure to control the overall type I error of 0.05. The secondary efficacy endpoints will be tested only if the primary efficacy assessment achieves significance, and following the hierarchy as below:

1. Superiority test of the change in body weight in subjects with baseline BMI ≥ 25 kg/m² in the bexagliflozin group compared with glimepiride group at week 60
2. Superiority test of the change in SBP in subjects with baseline SBP ≥ 140 mmHg in the bexagliflozin group compared with glimepiride group at week 60
3. Superiority test of the difference in proportion of subjects with ≥ 1 severe or documented symptomatic hypoglycemia events in the bexagliflozin group compared with glimepiride group over 96 weeks

The exploratory efficacy objectives and safety objectives will be analyzed descriptively.

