9.6 Secondary Efficacy Analyses

To assess the treatment effect on the change of body weight in subjects with baseline BMI ≥ 25 kg/m² at week 60, an analysis of covariance model (ANCOVA) will be implemented using all available data at week 60 (values obtained after the start of rescue medication will not be excluded in the analysis). The model will include treatment, randomization stratification factors, and the baseline weight value as fixed effects/covariates. Least squares mean treatment differences between the bexagliflozin group and the comparator group will be estimated from the model. The corresponding 95% CI and p-value will be provided.

The change in systolic blood pressure (SBP) in subjects with baseline SBP ≥ 140 mmHg in the bexagliflozin group compared with glimepiride group at week 60 will be analyzed using the same method.

The difference in proportion of subjects with ≥ 1 severe or documented symptomatic hypoglycemia events in the bexagliflozin group compared with glimepiride group over 96 weeks will be analyzed using logistic regression model which includes terms of treatment, randomization stratification. Odd ratio estimates, 95% two-sided confidence intervals and p-values for the treatment difference will be provided.

All analyses will be conducted in ITT analysis set. A hierarchical testing procedure will be applied to above three endpoints in the sequence provided above.

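### SAP 8.2 opens the body weight test on HbA1c non-inferiority, but SAP 8.2.1 makes its p-value non-inferential without HbA1c superiority (90.1% vs 2.5% chance of a formal test at a true difference of 0)

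*SAP*

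**What the plan says.** **The gate in SAP 8.2 and the Protocol.** SAP 8.2 states: "The secondary endpoints will only be tested when the non-inferiority of the primary efficacy assessment is established at one-sided significance level of 0.025". It lists body weight, SBP and hypoglycemia, in that order, and sets the level: "To control the overall type I error of 0.05, the secondary efficacy objectives will be tested at one-sided 0.025 significance level". Protocol 9.1 has the same gate and order: "The secondary efficacy endpoints will be tested only if the primary efficacy assessment achieves significance, and following the hierarchy as below". The Protocol synopsis (Statistical Methods) tests the secondary endpoints "in a hierarchical testing strategy and only if the primary objective is met" and numbers the same three steps. Protocol 9.6 gives the order without the gate: "A hierarchical testing procedure will be applied to above three endpoints in the sequence provided above".

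**The gate in SAP 8.2.1.** Body weight is to be tested if HbA1c non-inferiority "and the previous secondary efficacy endpoints are significant", although nothing precedes body weight in the 8.2 list. The same section adds that if HbA1c superiority "is not established, the nominal p-value will not be used for inferential purposes".

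**The status of HbA1c superiority.** It is the fourth secondary objective or endpoint in Protocol 2.2, SAP 3.2 and SAP 4.2. The synopsis sentence places it in the hierarchy: "the change in HbA1c from baseline at week 60 will be tested as key secondary endpoints and will be analyzed in a hierarchical testing strategy". No numbered sequence contains it. The synopsis, Protocol 9.1, Protocol 9.5.2 and SAP 8.1.1 all let it be declared directly when the upper 95% bound for HbA1c is below 0.

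**Recorded changes.** SAP 13 lists departures from the Protocol. A superiority gate for body weight is not among them.

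**The concern.** Suppose the upper 95% bound for HbA1c lies between 0 and 0.35. SAP 8.2 then permits a confirmatory body weight claim and SAP 8.2.1 forbids it. No precedence rule settles which applies, and a choice made after unblinding would be open to the charge that the data drove it.

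The uncertainty passes down the chain. SAP 8.2.2 makes SBP depend on a significant body weight result, and SAP 8.2.3 makes hypoglycemia depend on the earlier endpoints. Neither section repeats the superiority condition, so for them this is an inference from the chain.

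The extra condition in 8.2.1 costs chances of a formal test and does not inflate type I error. The opposite problem appears if 8.2.1 is set aside. HbA1c superiority is then claimed outside the chain while body weight is gated on non-inferiority only, which gives two separate routes to a false claim.

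**Working it through.** **Inputs (Protocol 9.2, SAP 3.8).** Margin 0.35, SD 1.0, one-sided 0.025, 90% power, 172 evaluable and 210 randomized per arm, 18% dropout. The true difference d (bexagliflozin minus glimepiride) is not stated.

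**Reproducing the plan's n.** With d = 0, n per arm = 2 × (1.960 + 1.2816)² × 1.0² / 0.35² = 171.5, rounded up to 172. Then 172 / 0.82 = 209.8, rounded up to 210. The stated figures therefore imply d = 0. A noncentral t calculation gives 89.9% power at 172, so the approximation is adequate.

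**Chance that each gate opens.** SE = √(2/172) = 0.1078.
- Non-inferiority gate: Φ((0.35 − d)/SE − 1.96)
- Superiority gate: Φ(−d/SE − 1.96)

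At d = 0 these are Φ(1.286) = 0.901 and Φ(−1.96) = 0.025. At d = −0.20 they are Φ(3.141) = 0.999 and Φ(−0.105) = 0.458.

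| Assumed d | Non-inferiority gate, 172 per arm | Superiority gate, 172 per arm | Non-inferiority gate, 210 per arm | Superiority gate, 210 per arm |
|---|---|---|---|---|
| +0.05 | 79.4% | 0.8% | | |
| 0 | 90.1% | 2.5% | 94.8% | 2.5% |
| −0.05 | 96.0% | 6.7% | | |
| −0.10 | 98.7% | 15.1% | 99.6% | 17.5% |
| −0.20 | 99.9% | 45.8% | >99.9% | 53.6% |
| −0.30 | >99.9% | 79.4% | | |
| −0.35 | >99.9% | 90.1% | >99.9% | 94.8% |

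The 210 columns assume every randomized subject is evaluable (SE = 0.0976). Superiority implies non-inferiority, so the chance that the two rules conflict is the difference between the columns. At 172 per arm this is 90.1 − 2.5 = 87.6% at d = 0 and 99.9 − 45.8 = 54.1% at d = −0.20.

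**Chance of at least one false claim.** Take d = 0, no body weight effect, one-sided 0.025 per test and 172 per arm.
- Superiority outside the chain, body weight gated on non-inferiority, independent statistics: 0.025 + (0.9007 − 0.025) × 0.025 = 0.0469. With correlation 0.1, 0.2, 0.3 and 0.5 it is 0.0474, 0.0475, 0.0472 and 0.0453. At 210 per arm the range is 0.0454 to 0.0482.
- Superiority placed before body weight: 0.0250.
- Superiority last, or nominal only: 0.9007 × 0.025 = 0.0225, rising to 0.0249 at correlation 0.5.

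**The case against.** **The superiority wording may be a slip.** SAP 8.2.1 opens with non-inferiority, and the later word could be an error for it. SAP 8.1.1 has comparable leftovers: a placebo group in an active-controlled trial, and week 24 values for a week 60 endpoint. This is plausible but cannot be shown from the documents, and it leads to the same edit of 8.2.1.

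**The lists already suggest an order.** Every list puts HbA1c superiority fourth. That supports making it the last step. It does not settle the matter, because no testing sequence includes it and four sections allow it to be declared directly.

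**The 90.1% against 2.5% contrast is design power beside alpha.** That is true at d = 0, where any superiority gate opens 2.5% of the time, so a range is needed. The unadjusted SD also matters. If baseline adjustment cut the residual SD to 0.9 or 0.8 (an assumption), the superiority gate at d = −0.20 would open 54% or 64% of the time instead of 45.8%. The gap narrows but remains.

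**The 4.7% arises only if 8.2.1 is ignored.** This is correct: with the 8.2.1 condition in force the figure is 2.5%. It is therefore a reason not to delete that sentence in isolation. Assumed negative correlations of −0.3 and −0.5 would lower it to 4.3% and 3.9%, still above 2.5%. It is a one-directional rate, so the SAP's overall 0.05 is not the right comparator.

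**The primary test is untouched and the stricter reading is conservative.** Both statements stand. They do not tell the analyst which rule governs the first secondary claim.

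**Conclusion.** The contradiction is real, stands in current SAP text, and is not recorded as a change from the Protocol. If HbA1c superiority is the earlier endpoint that 8.2.1 has in mind, its sequence is coherent: non-inferiority, superiority, body weight, SBP, hypoglycemia. It is simply not the sequence in SAP 8.2, Protocol 9.1 or the synopsis list.

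At the implied difference of 0 the two rules would conflict in about 88% of trials, and at an assumed −0.20 in about 54%. These figures rest on the design-stage normal approximation with 172 evaluable per arm and SD 1.0. The planned mixed-model analysis, with or without multiple imputation, may have different precision. Power for body weight itself was not calculated.

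This must be settled before unblinding, because it leaves the confirmatory path undefined in the result the design expects. The status of HbA1c superiority has to be settled in the same edit.

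**What to change.** Choose one of two routes before unblinding.

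**Route A: align 8.2.1 with SAP 8.2 and Protocol 9.1.**
1. In 8.2.1, delete the reference to previous secondary endpoints and the sentence that makes the p-value non-inferential without HbA1c superiority. Body weight is then tested once HbA1c non-inferiority is established at one-sided 0.025.
2. In SAP 8.2, give HbA1c superiority one explicit status: a fixed step in the sequence, or nominal only. As the last step, its claim depends on body weight, SBP and hypoglycemia all being significant. As nominal only, the confirmatory claim is given up.
3. Amend the direct declaration in SAP 8.1.1 to match. Record in SAP 13 that the choice overrides the direct declarations in the synopsis, Protocol 9.1 and Protocol 9.5.2. If superiority becomes a step, also record that it extends the three endpoints of Protocol 9.6.

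**Route B: keep superiority ahead of body weight.** Retain the 8.2.1 condition, list HbA1c superiority as the first step in SAP 8.2, and record the change in SAP 13. The price is the reduced chance of testing body weight shown in the table.

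As a wording point only, 8.2.2 should say that the confirmatory SBP test is in subjects with baseline SBP of at least 140 mmHg, since its text also refers to all subjects.

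**Cost.** A text amendment to SAP 8.2, 8.2.1 and 13, with 8.1.1 under Route A, plus one phrase in 8.2.2. Protocol 9.1 makes the SAP the final plan, so a section 13 entry can carry the override. No extra subjects or data are needed.
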